Individual Placement and Support (IPS) to increase employment. Increasing employment is critical both to reduce poverty and unemployment, risk factors for injection drug use and HIV; and to facilitate the success of the Therapeutic Workplace's Abstinence-Contingent Wage Supplement Model. Employment interventions for unemployed drug users have been consistently ineffective (Magura et al., 2004). Notably, a multi-site study by the NIDA Clinical Trials Network of the Job Seekers Workshop failed to show any effect of that intervention (Svikis et al., 2012). Therapeutic Workplace participants are employed at significantly higher rates after participation in the Therapeutic Workplace than before, but still only about 20% of participants work at fulltime after Therapeutic Workplace participation (Sigurdsson et al., 2011). To increase employment, we will combine the Therapeutic Workplace with the Individual Placement and Support (IPS) model of supported employment. IPS was designed to promote competitive employment in persons with severe mental illness. IPS is a common-sense employment intervention that involves rapid job search, promotes competitive employment, considers the participant's preferences, and provides job supports and benefits counseling. IPS is implemented by employment specialists who establish relationships with potential employers, and work with participants individually and in groups to identify available jobs, prepare applications, and to apply for positions. Employment specialists also provide support to participants during employment to increase success in a job. IPS is offered on a long-term

basis, with expectation that participants may need assistance repeatedly over time. IPS has been shown effective in increasing employment across many U.S. states, across several countries, and across a variety of economic conditions (Bond et al., 2012). A secondary analysis showed that IPS produced significant increases in employment in a subset of individuals who were dually diagnosed with severe mental illness and a substance use disorder (Mueser et al., 2011). We will adapt IPS to promote employment in participants after they initiate abstinence and acquire basic job skills in the Therapeutic Workplace. The developer of IPS ([name]), a co-investigator on this grant, will oversee IPS implementation. This study will be the first application of this proven employment intervention in low-income injection drug users.

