during the intervention evaluation period. This number of stratification variables has been sufficient to balance groups in past studies.

Individual Placement and Support (IPS) & Abstinence-Contingent Wage Supplement Group

This study will evaluate a novel intervention designed to promote long term employment and drug abstinence. The intervention will combine Individual Placement and Support with abstinence-contingent wage supplements. This group will receive the full intervention being evaluated in this study for one year.

Individual Placement and Support (IPS). To increase employment, after completing Phase 1 of the Therapeutic Workplace, participants will be offered Individual Placement and Support (IPS) model of supported employment for one year. IPS involves rapid job search, promotes competitive employment, considers the participant's preferences, and provides job supports and benefits counseling. The employment specialist will establish relationships with potential employers and work with participants to identify potential jobs, prepare applications, and to apply for positions. The employment specialist will provide IPS under the supervision of [name] (Co-I), the developer of IPS, and [name] (Consultant).

Fidelity measures will be collected to ensure that IPS is followed consistently. Using the procedures outlined by Bond, Peterson, Becker and [name] (2012), two trained IPS assessors will visit our research unit for 1.5 days per year and use IPS-25 to assess IPS fidelity. IPS-25 consists of 25 items that specify critical features of IPS. Each item is rated on a 5-point scale which represents the degree to which the program adheres to that feature of IPS. The assessors will interview our staff and our employment specialist, observe team meetings and community contacts with employers, interview clients, and review client charts. After the site visit, the assessors will independently make fidelity ratings and then reconcile discrepancies. The assessors will also prepare a fidelity report and provide recommendations for improvement. IPS-25 fidelity scores have been shown to be significantly associated with rates of employment (Bond et al., 2012). This fidelity assessment process has led to programs attaining good fidelity across hundreds of implementations.

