Resetting the wage supplement value. Participants will continue to be eligible to earn the maximum in abstinence-contingent wage supplement as long as they continue to provide opiate- and cocaine-negative urine samples on all required sample collection days. If a participant ever fails to provide a scheduled sample or provides a urine sample that is positive for opiates or cocaine, the value of the wage supplement will be reduced to \$1.00 per hour and the frequency of required urine collections will be increased to the initial frequency of two days per week on average. The value of the wage supplement will

be increased by \$1.00 per hour for every day that the participants provide a drug negative sample. In addition, the probability of required urine sample collections will be gradually decreased again as long as the participant continues to provide drug-negative urine samples on required urine collection days. By the end of the year, participants should be required to provide urine samples on one randomly selected Monday, Wednesday or Friday every two weeks.

Individual Placement and Support (IPS) Only Group

Participants assigned to the Individual Placement and Support (IPS) Only group will receive the IPS intervention as described above. This group will receive IPS as it has been implemented thus far for people with severe mental illness. Participants in this group will not receive the monetary incentive for performing IPS tasks or maintaining competitive employment (wage supplement).

Intake, Outcome & Economic Assessments

For the primary aim of the study, assessments will be conducted at intake, every 30 days throughout the 3-month abstinence initiation period, every 30 days throughout the 12-month intervention evaluation period after random assignment and then at 3, 6, 9 and 12 months after the end of the intervention evaluation period. Assessments will be administered using Qualtrics, a web-based software (<http://qualtrics.com/>) to administer and record responses for the questionnaires administered that we are using in our other protocols. If the Qualtrics is not available, we may administer assessments using paper forms. The paper versions of the assessments are included in the section 19 for Supplemental Study Documents. Urine samples will be collected at each of these time points and we may test for cocaine, opiates, marijuana, amphetamines, methamphetamines, methadone, buprenorphine, barbiturates, benzodiazepines, MDMA, PCP, and oxycodone.

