
To gain verified and objective records of employment, we may get an objective measure of each participant's employment history by getting each participant's earnings history using federal Form SSA-7050-F4 (10-2016) UF, REQUEST FOR SOCIAL SECURITY EARNINGS INFORMATION. Participants and research staff will complete this form and have the participant's earnings history sent to our research unit. Our research unit will pay for the costs of this service. We may request these documents one or more times. We will take the following steps to protect this sensitive information in our study databases (see also Section 8b): (1) when storing a completed form, we will redact name, date of birth, and social security number from the written document and label the document with an ID number; (2) keep paper copies in a locked file cabinet in a locked office and never keep documents out while unattended by research staff; (3) only enter relevant information into the database (i.e., information about when participants worked, how much they earned, and what type of employment they had); and (4) maintain a confidentiality certificate from the NIH. The risks associated with collecting this information are explained on the consent form.

a. Study duration and number of study visits required of research participants.

Participants will be invited to attend Phase 1 of the therapeutic workplace every weekday for 3 months. Participants in the immediate-work group will attend for 4 hours every weekday. Participants in the delayed work group will be asked to come to the workplace every day for a brief visit (30 minutes or less) to complete study measures for the first 3 weeks and then for the full 4 hours for the remainder of the 3 month period of Phase 1. All participants that report to be assessed at the end of Phase 1 will be randomly assigned to the primary study groups and offered Individual Placement and Support for 1 year. The IPS intervention is designed to promote employment in competitive community workplaces. All participants will be invited to participate in an intake assessment to determine eligibility and characterize the population. Outcome assessments will be conducted every 30 days throughout the 3-month abstinence initiation period, every 30 days throughout the 12-month intervention evaluation period after random assignment, and then at 3, 6, 9 and 12 months after the end of the intervention evaluation period.

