b. Blinding, including justification for blinding or not blinding the trial, if applicable.

NA

c. Justification of why participants will not receive routine care or will have current therapy stopped.

NA

d. Justification for inclusion of a placebo or non-treatment group.

NA

e. Definition of treatment failure or participant removal criteria.

Participants will be removed from the study if they threaten the safety of CLH staff or other research participants, or of any other persons on the Johns Hopkins Bayview Campus.

f. Description of what happens to participants receiving therapy when study ends or if a participant's participation in the study ends prematurely.

Throughout the study, participants will be given referrals to services they might need (e.g., drug counseling, housing, medical, or employment services).

5. Inclusion/Exclusion Criteria

Inclusion criteria: a) ≥ 18 yrs old; b) unemployed; c) provide an opioid-positive (methadone, buprenorphine, or morphine) urine sample at intake; e) in methadone or buprenorphine treatment or meet DSM criteria for heroin dependence; and g) express interest in obtaining competitive employment.

Exclusion criteria: a) report current suicidal/homicidal ideation; b) have a severe psychiatric disorder.

6. Drugs/ Substances/ Devices

a. The rationale for choosing the drug and dose or for choosing the device to be used.

NA

b. Justification and safety information if FDA approved drugs will be administered for non-FDA approved indications or if doses or routes of administration or participant populations are changed.

NA

c. Justification and safety information if non-FDA approved drugs without an IND will be administered.

NA

7. Study Statistics

We will compare the *IPS* Plus Abstinence-Contingent Wage Supplement and *IPS* Only participants on primary, secondary and economic measures. Each measure is associated with a *Specific Aim*.

a. Primary outcome variable.

Specific Aim. Assess the effectiveness of the *IPS* Plus Abstinence-Contingent Wage Supplements in preventing relapse to heroin and cocaine. We will assess rate of urine samples negative for opiates and cocaine at the 12 monthly assessments during the year after random assignment (Y/N at each assessment).

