Specific Aim. Assess the effectiveness of the *IPS* Plus Abstinence-Contingent Wage Supplements in promoting employment. We will assess rate that participants report being employed at the 12 monthly assessments during the year after random assignment (Y/N at each assessment).

b. Secondary outcome variables.

Specific Aim. Assess the effectiveness of the *IPS* Plus Abstinence-Contingent Wage Supplements in reducing injection drug use. We will assess the rate that participants report injecting drugs in the past 30 days at the 12 monthly assessments in the year after random assignment (Y/N at each assessment).

Specific Aim. Assess the effectiveness of the *IPS* Plus Abstinence-Contingent Wage Supplements in reducing drug-related HIV risk behaviors. We will assess the rate that participants report sharing injection equipment (needles/syringes without disinfecting, cookers/cottons/rinse water, or drug solution) or trading unprotected sex for drugs or money in the past 30 days at the 12 monthly assessment during the year after random assignment (Y/N at each assessment). If the *IPS* Plus Abstinence-Contingent Wage Supplements reduces cocaine and opiate use, it should reduce these risk behaviors.

Specific Aim. Assess the effectiveness of the *IPS* Plus Abstinence-Contingent Wage Supplements in reducing family poverty. We will assess whether family income is at or below the federal poverty level at the 12 monthly assessments during the year after random assignment (Y/N at each assessment) with and without wage supplement earnings. *IPS* Plus Abstinence-Contingent Wage Supplements should reduce poverty.

Specific Aim. Assess the effectiveness of the *IPS* Plus Abstinence-Contingent Wage Supplements in promoting long-term drug abstinence and employment and in reducing HIV risk. We will compare the groups on all measures of heroin and cocaine use, employment, and HIV risk behaviors at 3-, 6-, 9- and 12-month follow-up assessment time points after *IPS* and abstinence-contingent wage supplements have ended.

Specific Aim. *Assess the costs of treatment for IPS Only and IPS Plus Abstinence-Contingent Wage Supplements.* We will assess the total cost per participant of both study interventions. We expect that treatment costs for IPS Plus Abstinence-Contingent Wage Supplements will be higher per person relative to the IPS Only due to the wage supplements and because we expect that IPS Plus Abstinence-Wage Supplement participants will have greater treatment engagement.

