The primary outcome measures will be analyzed with a longitudinal logistic regression model using GEE (Diggle et al., 2002). We used Liu and Liang (1997) to determine the total N required to detect differences between groups with 80% power. The adjacent figure shows the total number of participants (N) that would be required to detect a difference of 15% between the IPS Only and the IPS Plus Abstinent-Contingent Wage Supplement with the 12 monthly assessments. The adjacent figure shows possible percentages for the IPS Only group because that value affects the sample size required. Fifteen percent is smaller than any difference in any Therapeutic Workplace study in which we promoted cocaine abstinence in methadone patients. This difference is also smaller than any difference between Control and IPS groups in the percentage of participants that become employed. Based on this, we need a maximum of 120 participants (horizontal dashed line) to detect a difference between the IPS Only and the IPS Plus Abstinent-Contingent Wage Supplement groups of 15% or more on each primary outcome.

Statistical Analyses

Main analysis. All measures assessed repeatedly over time will be analyzed with a longitudinal logistic regression model. Within-person correlated outcomes will be handled using generalized estimating equations (GEE; Zeger et al., 1988). Measures assessed once will be analyzed using logistic regression. The magnitude of effect for both logistic regression and GEE will be expressed using odds ratios with 95% CI. Analyses will include all randomized participants as intent-to-treat, and will be adjusted for pre-specified covariates used for stratification (Pocock et al., 2002). Tests will be two-sided and p-values <.05 will be considered significant.

Moderator analyses. We will conduct analyses to identify variables that moderate the outcomes of our two primary outcome measures, employment and drug (opiates and cocaine) abstinence. We will examine differences in efficacy as a function of two variables assessed prior to random assignment by including interaction terms in our regression models: 1) Percentage of urine samples negative for opiates and cocaine at the three monthly urine samples collected prior to random assignment. 2) Completed high

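### Does citing Control-versus-IPS differences, when both arms receive IPS, undermine the 15-point employment difference or the sample size of 120?

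*Combined protocol and SAP*

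**What the plan says.** Section 7c (Power Analysis) takes 15 percentage points as the difference to be detected between IPS Only and IPS plus wage supplements, with 80% power, 12 monthly assessments and at most 120 participants in total. Required N is plotted against possible IPS Only percentages in a figure that is not reproduced. For abstinence, the text says that earlier Therapeutic Workplace studies all found larger differences. For employment it says: "This difference is also smaller than any difference between Control and IPS groups in the percentage of participants that become employed".

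Both arms receive IPS. Section 4 says of the supplement group that "participants will be offered Individual Placement and Support (IPS) model of supported employment for one year", and of the comparator: "Participants assigned to the Individual Placement and Support (IPS) Only group will receive the IPS intervention as described above". Section 4a says the same of everyone who reports for assessment at the end of Phase 1: they are "randomly assigned to the primary study groups and offered Individual Placement and Support for 1 year".

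The employment endpoint in Section 7a is repeated status: "We will assess rate that participants report being employed at the 12 monthly assessments during the year after random assignment".

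Section 7c (Missing data) expects more than 90% of assessments to be collected and scores missing values as the adverse outcome in the primary approach. It compares the estimates with an analysis without imputation and treats conclusions as tentative if the two differ.

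**The concern.** The employment benchmark differs from this trial in three ways.

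- **Contrast.** The cited differences compare IPS with no IPS. Here the randomised difference is the wage supplement.
- **Endpoint.** The benchmark counts people who become employed. The endpoint is employment at each of 12 monthly assessments.
- **Population.** Section 3 states: "This study will be the first application of this proven employment intervention in low-income injection drug users". Section 4 says of the comparator: "This group will receive IPS as it has been implemented thus far for people with severe mental illness". Section 5, however, excludes people who "have a severe psychiatric disorder".

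The documents give no effect size for supplements added to IPS. Section 3 cites wage supplements raising employment in welfare recipients, but without a number. A reader could therefore take 15 points as a cautious choice backed by evidence when, for employment, it is an assumption.

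The second worry is dilution. Scoring missing values as adverse pulls both arms' rates towards zero and shrinks the difference between them. If 15 points is the difference before that scoring, the stated 80% may not describe the primary analysis. One of two primary outcomes would then rest on a weaker power claim than it seems to.

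**Working it through.** **Inputs.** From Section 7c: two-sided 5% test, 80% power, difference d = 0.15, 12 assessments, N = 120, less than 10% missing. Assumed: 60 per arm (no ratio is stated) and a constant within-person correlation ρ. The control rate p0 is varied because the plan's range is in the missing figure.

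**1. Reproducing 120.** For a repeated binary outcome,

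N = 2(1.96 + 0.8416)² × (p0q0 + p1q1) × (1 + 11ρ) / (12d²).

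With nothing missing, the least favourable pair is 42.5% against 57.5%, where p0q0 + p1q1 = 0.48875. The part without the repeats factor is 2 × 7.849 × 0.48875 / 0.0225 = 341. Setting 341 × (1 + 11ρ)/12 = 120 gives 1 + 11ρ = 4.223, so ρ = 0.293. If 120 is enough at every control rate, 0.293 is the largest correlation the plan can have used. At ρ = 0.20 the same formula gives N = 341 × 3.2/12 = 91, and 120 participants have 90% power. The figure 120 is attainable. The readable text can neither confirm nor refute it.

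**2. Smaller employment effects, nothing missing.** Power = Φ(d/SE − 1.96), with SE² = (p0q0 + p1q1)(1 + 11ρ)/(12 × 60). For 12 points at p0 = 42.5% and ρ = 0.293, SE = 0.0537 and power = Φ(2.233 − 1.96) = 61%.

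| True difference | p0 42.5%, ρ 0.293 | p0 20%, ρ 0.293 | p0 42.5%, ρ 0.20 | p0 20%, ρ 0.20 |
|---|---|---|---|---|
| 12 points | 61% | 72% | 73% | 83% |
| 10 points | 46% | 57% | 57% | 69% |

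The 10 and 12 points are illustrations. Nothing in the documents makes them likelier than 15 or more, and any trial sized for 15 points loses power below it.

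**3. Missing scored as adverse.** Take 10% missing, equal between arms and unrelated to outcome, with 15 points as the difference before scoring. The rates become 0.9 × 42.5% = 38.25% and 0.9 × 57.5% = 51.75%, a difference of 13.5 points.

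With sporadic missingness, the variance of a participant's 12-month mean is [0.9p + 11 × 0.81(p² + ρpq)]/12 − (0.9p)². At ρ = 0.293 this is 0.0728 for p = 0.425 and 0.0740 for p = 0.575. So SE = √(0.1468/60) = 0.0495, and power = Φ(0.135/0.0495 − 1.96) = 78%.

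Even dropout means that 0.10 × 12/6.5 = 18.5% of participants leave, at visits spread evenly over the year.

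| Control rate, ρ | Sporadic | Even dropout |
|---|---|---|
| 42.5%, 0.293 | 78% | 69% |
| 42.5%, 0.20 | 87.5% | 78.5% |
| 20%, 0.293 | 87% | 83% |

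The choice of 0.293 sets undiluted power at exactly 80% for a 42.5% control rate, so any dilution must fall below 80% there. With 5% sporadic missing instead of 10%, power is 79% even in that case. The plan expects less than 10%, so 10% is the upper end.

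**4. Abstinence.** Section 3 reports 79.3% against 50.7% cocaine-negative samples in a relevant earlier trial, a difference of 28.6 points. Even if 10% of participants are lost entirely and scored adverse, power at that contrast is 99% (ρ = 0.293).

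**The case for a change.** The strongest case for a change starts from where the sentence sits. It is the only support Section 7c gives for the employment difference, and the text then draws the sample size from it. If employment shows no difference, a reader relying on that section could think the trial was powered for less than every known relevant effect, when the effect of supplements added to IPS had no number behind it. The correction would be a few sentences. The dilution can also be worse than at 42.5%, which is the least favourable control rate only when nothing is missing. Under even dropout at correlation 0.293, power is about 67% near a 55% control rate.

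Part of this stands. The cited contrast is not the randomised one, and a more exact author would have called 15 points the assumed or smallest difference of interest. The benchmark is not irrelevant, though. Section 4 expects supplements to raise engagement with IPS, and Section 3 reports an IPS benefit in people with both severe mental illness and a substance use disorder. Section 7c never uses the word conservative; it says that 120 participants can detect 15 points or more, and that claim does not depend on the benchmark. A null result would be read from the odds ratio and its 95% confidence interval, which the plan already requires. The dilution point needs an unfavourable correlation, control rate and missingness pattern together, and needs 15 points to be the difference before scoring. None of these can be established from the readable text.

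**Conclusion.** No change follows. The mismatch is real but is a matter of wording, and it concerns employment only. Calling 15 points an assumption would leave the 120 participants, the GEE analysis and every result as they are. Whether 15 points is before or after adverse scoring is a missing detail that analysts can settle when they report, and the planned comparison with the unimputed analysis already covers robustness to the scoring rule.

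On size: if 15 points is before scoring, 10% missing equally and unrelated to outcome makes it 13.5. For the control rates of 20%, 42.5% and 55% discussed here, power under sporadic missingness or even dropout then runs from about 67% (correlation 0.293, even dropout, control rate near 55%) to above 80% (for example 87.5% at correlation 0.20, sporadic, 42.5%). If 15 points is already after scoring, there is no dilution. These figures rest on 60 per arm, a constant correlation and values of it that the readable text does not give. Neither 120 nor the stated 80% is shown to be wrong.

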4. Study Procedures

Procedures for COVID-19

We will complete the remaining assessments without any in person contact. Interviews will be conducted over the phone and when possible we will obtain urine sample results from each participant's clinic. To do that, participants can ask their clinic to send us their urinalysis results. If needed, we will mail a re-loadable credit card to participants.

Recruitment Procedures

Identifying, Screening and Consenting Participants

Participants will be recruited from methadone and buprenorphine programs in Baltimore using procedures that we have used in prior evaluations of the Therapeutic Workplace (Donlin et al., 2008; [name] et al., 2007). First, we will inform staff at methadone and buprenorphine treatment programs in Baltimore about the study and encourage them to refer potential participants to us. Second, we will post flyers and distribute business cards and information sheets with our toll-free number in each of these programs. Copies of the proposed flyer, business card and information sheets are enclosed with this application. Third, we will visit programs and recruit for the study onsite at each program. Fourth, as in our previous studies, participants will have the optional opportunity to earn incentives for referring people who are interested in the study. If a referral attends the initial screening appointment and completes the necessary assessments, the participant who referred the person will receive up to \$20. If a referred person enrolls in the main study, the participant who referred the person will receive up to \$40 for making the referral.

Experimental Design and Groups

Phase 1 Abstinence Initiation and Job Skills Training

All participants will be invited to attend Phase 1 of the Therapeutic Workplace for about 3 months where they can earn up to about \$40 every weekday and provide urine samples every Monday, Wednesday and Friday. To engage participants, both groups will be allowed to earn wages independent of their urinalysis results for the first 5 weeks.

Delayed Work vs. Immediate Work group. To assess the potential value of working in the workplace every weekday, upon enrollment in the study participants will be randomly assigned to a delayed work group or to an immediate work group. The delayed work participants will be paid a daily wage of \$40 for coming to the workplace to sign in and provide a urine sample (on Mondays,

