Review and expungement of criminal record. Criminal records are a major barrier to competitive employment in adults with a history of illicit drug use. To help participants prepare for competitive employment, we may collaborate with community partners (e.g., Maryland Legal Aid) who offer free legal assistance to participants in Phases 1 and 2. This assistance typically consists of determining eligibility for expungement, processing petitions for expungement of criminal records, and other free services approved by the legal team. Participants are notified by research staff that legal assistance is available, and that participation is voluntary. We may collect data to describe and evaluate the expungement process so we may better understand legal barriers to employment in adults with a history of illicit drug use. The data we would collect are the types of offenses participants have on their public records (i.e., records available to potential future employers), the number of convictions on record, which records are eligible or ineligible for expungement, whether petitions for expungement are filed by the legal team, whether petitions for expungement are granted or require a hearing, and how long it takes for participants to have their records expunged. We may publish an article to describe the expungement process and de-identified data of our participants. All data that we collect and publish on the criminal histories of our participants will be data that are publicly available.

Random Assignment

Participants (N = 120) will be randomly assigned to an IPS Only (Control) or IPS Plus Abstinence-Contingent Wage Supplements group. A computerized urn randomization procedure (Wei & Lachin, 1988) will be used to balance groups on three baseline characteristics that may influence outcome: (1) percentage of the three monthly urine samples collected prior to random assignment that are positive for cocaine (\geq rolling median, Y/N); (2) percentage of the three monthly urine samples collected prior to random assignment that are positive for opiates (\geq rolling median, Y/N); and (3) completed high school or obtained a GED (Yes/No). Participants will be stratified by cocaine and opiate use because drug use at random assignment should predict abstinence from opiates and cocaine and possibly employment during the intervention evaluation period. High school completion or GED should be associated with employment

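### The primary models measure pre-randomisation drug use by three monthly urines although up to about 36 are scheduled, so a modest gain in power, mainly for abstinence, goes unused

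*Combined protocol and SAP*

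**What the plan says.** Section 7.c, Main analysis, fits longitudinal logistic GEE models and states: "Analyses will include all randomized participants as intent-to-treat, and will be adjusted for pre-specified covariates used for stratification". Section 4, Random Assignment, lists three such covariates: "percentage of the three monthly urine samples collected prior to random assignment that are positive for cocaine", the same for opiates (each classed Y/N against a rolling median), and high-school or GED completion. No other baseline term is named for the main models.

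Section 4, Phase 1, has all participants "provide urine samples every Monday, Wednesday and Friday". Section 4.a adds: "Participants will be invited to attend Phase 1 of the therapeutic workplace every weekday for 3 months". Section 10 gives the length as 12 weeks. Random assignment comes at the end of Phase 1, so this whole series is pre-randomisation data.

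On prognosis, Random Assignment expects drug use at that point to predict abstinence and perhaps employment. The Moderator analyses in 7.c go further and expect earlier opiate and cocaine use to go with lower employment in the following year. Neither place gives a correlation.

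For power, 7.c sets out to "determine the total N required to detect differences between groups with 80% power" and concludes that "we need a maximum of 120 participants (horizontal dashed line) to detect a difference" of 15 points or more on each primary outcome. The readable text takes no credit for covariate adjustment.

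**The concern.** A percentage from three samples can take only four values (0, 1/3, 2/3, 1) and is a noisy measure of how often a person uses. Adjusting for a noisy measure removes only part of the variation between people that a better measure would remove. The trial already schedules a much denser record of the same behaviour, before random assignment and in both groups. At stake is power in a trial of 120; the validity of the planned test is not in question.

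**Working it through.** **1. The plan's own figure.** Inputs from 7.c: 80% power, two-sided 0.05, a 15-point difference, 12 monthly assessments. The within-person correlation ρ and the control rates are only in a figure that is not shown, so I take worst-case rates of 42.5% v 57.5%, 1:1 allocation, and solve for ρ.

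N = 2(z₀.₉₇₅ + z₀.₈₀)² [p₁q₁ + p₂q₂][1 + 11ρ] / (12 d²)

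With ρ = 0.29: 2 × 7.849 × 0.4888 × 4.19 / (12 × 0.0225) = 119.1. Control rates of 30-60% imply ρ of 0.29-0.35 at N = 120. The stated 120 is therefore plausible, but it cannot be confirmed from the readable text.

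**2. Count of unused samples.** 3 per week × 12 weeks = 36. This is a ceiling, because samples depend on participants coming in.

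**3. Gain for abstinence.** I simulated 5,000 trials per setting: N = 120, 41% v 57% negative, outcome within-person correlation about 0.3, two drugs, logistic GEE with robust standard errors, no missed samples. Here r is the assumed correlation between drug-use propensity in Phase 1 and in the outcome year.

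| r | Planned Y/N covariates | Three-urine percentages | 36-urine percentages | Gain over three-urine percentages |
|---|---|---|---|---|
| 0 | 76.9% | 76.7% | 77.0% | 0.3 |
| 0.3 | 78.5% | 78.9% | 79.6% | 0.7 |
| 0.5 | 81.0% | 82.4% | 85.1% | 2.7 |
| 0.7 | 84.0% | 86.9% | 91.2% | 4.3 |

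The last column is the one that matters here. The step from the Y/N covariates to three-urine percentages comes from undoing the median split and needs no extra samples. Other versions of the simulation gave gains of about 1 point at r = 0.3, 2-3 at 0.5 and 4-6 at 0.7, hence the range of 2-6 points at r = 0.5-0.7.

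**4. Power or precision?** Moving from three-urine to 36-urine percentages:
- r = 0.5: mean standard error 0.225 to 0.222 (down 1.3%); mean log odds ratio 0.650 to 0.664 (up 2.2%).
- r = 0.7: 0.218 to 0.211 (down 3.2%); 0.679 to 0.708 (up 4.3%).

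More of the gain comes from the larger conditional odds ratio than from a narrower interval.

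**5. Missed samples.** If, as an assumption, 30% of samples are missed and counted as not negative, the gain falls by up to half, to about 1-2 points at r = 0.5. Scoring only the samples provided, or adding a proportion-provided term, largely recovers it.

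**6. Type I error.** With no treatment effect (3,000 trials per setting), rejection stayed between 4% and 6% under every covariate set, including the planned one.

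**7. Employment.** From 80% power, an extra R² gives Φ(2.80/√(1 − R²) − 1.96): 80% at R² = 0, 82% at 0.05, 84% at 0.10. Nothing in the documents selects a value, so this is a conversion and not an estimate.

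**The case against.** The planned adjustment is standard and valid, and the stated power does not rely on it. Choosing further predictors can be called a matter of taste. That stands as far as validity goes: this is an improvement to consider, not an error to correct.

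The correlation may also be low. Phase 1 abstinence is partly under a pay contingency that the IPS Only group then loses, and Section 4 starts that contingency after varying durations, so the 36 samples do not come from one uniform condition. That stands too, and it is why the range starts at zero.

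A reader might infer that both primary comparisons demonstrably lose precision. The documents do not support this. For employment they offer an expectation about earlier drug use and no figure. No passage links Phase 1 attendance, which is itself paid, to later employment, so a work-hours covariate has no documented basis. Nor is a clear narrowing of the confidence intervals supported, given step 4 of the working.

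Lastly, the document is dated March 2022, its COVID-19 section speaks of completing the remaining assessments, and its blinding entry is not applicable. Adding primary covariates this late is free of selection only if it is done without sight of outcomes by group.

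**Conclusion.** The concern holds as a missed efficiency. The primary models use three monthly urines as the drug-use baseline although up to about 36 scheduled pre-randomisation samples could inform it. For abstinence the gain over three-urine percentages is about 0-1 power points at an assumed correlation of 0-0.3 and about 2-6 points at 0.5-0.7, less if many samples are missed and scored as not negative. The size rests on that assumed correlation, an outcome within-person correlation near 0.3, and a true difference of about 15 points. For employment a gain is possible, because 7.c expects earlier drug use to be predictive, but it cannot be sized. The planned analysis remains valid without the change.

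**What to change.** In 7.c, keep the stratification covariates and add three continuous terms to both primary GEE models:

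- the proportion of provided Phase 1 Monday/Wednesday/Friday samples that are negative for cocaine;
- the same for opiates;
- the proportion of scheduled samples provided.

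The third term separates missed samples from drug use and serves as the attendance measure, so no work-hours term is needed. Count as scheduled only the days on which a sample was actually required, and state a rule for anyone who provided none.

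Set this out in a dated amendment made without sight of outcomes by group. If outcomes have already been analysed, keep the planned model as primary and report this one as a labelled sensitivity analysis.

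The cost is SAP wording, a merge of the Phase 1 urine data, three more terms in each model, and an odds ratio that is conditional on more covariates and should be described as such.
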